#### d. Results in persistent or significant disability/incapacity

- The term disability means a substantial disruption of a person's ability to conduct normal life functions
- This definition is not intended to include experiences of relatively minor medical significance such as uncomplicated headache, nausea, vomiting, diarrhea, influenza,

and accidental trauma (eg, sprained ankle) that may interfere with or prevent everyday life functions but do not constitute a substantial disruption.

#### e. Is a congenital anomaly/birth defect

• In offspring of participant taking the product regardless of time to diagnosis.

#### f. Other important medical events

• Medical or scientific judgment should be exercised in deciding whether SAE reporting is appropriate in other situations such as important medical events that may not be immediately life-threatening or result in death or hospitalization but may jeopardize the participant or may require medical or surgical intervention to prevent 1 of the other outcomes listed in the above definition. These events should usually be considered serious.

Examples of such events include invasive or malignant cancers, intensive treatment in an emergency room or at home for allergic bronchospasm, blood dyscrasias or convulsions that do not result in hospitalization, or development of drug dependency or drug abuse.

#### 10.3.3 Additional Events Reported

#### Additional events that require reporting

In addition to the above criteria, AEs meeting either of the below criteria, although not serious per ICH definition, are reportable to the Sponsor.

- Is a cancer
- Is associated with an overdose

#### 10.3.4 Recording AE and SAE

#### **AE and SAE recording**

- When an AE/SAE occurs, it is the responsibility of the investigator to review all documentation (eg, hospital progress notes, laboratory, and diagnostics reports) related to the event.
- The investigator will record all relevant AE/SAE information on the AE CRFs/worksheets at each examination.
- It is not acceptable for the investigator to send photocopies of the participant's medical records to the Sponsor in lieu of completion of the AE CRF page.
- There may be instances when copies of medical records for certain cases are requested by the Sponsor. In this case, all participant identifiers, with the exception of the participant

V114-030-00 FINAL PROTOCOL 27-MAR-2019

number, will be blinded on the copies of the medical records before submission to the Sponsor.

• The investigator will attempt to establish a diagnosis of the event based on signs, symptoms, and/or other clinical information. In such cases, the diagnosis (not the individual signs/symptoms) will be documented as the AE/SAE.

#### **Assessment of intensity**

- An event is defined as "serious" when it meets at least 1 of the predefined outcomes as described in the definition of an SAE, not when it is rated as severe.
- The investigator will make an assessment of intensity for each AE and SAE (and other reportable safety event) reported during the study and assign it to 1 of the following categories:
  - Mild: An event that is easily tolerated by the participant, causing minimal discomfort and not interfering with everyday activities (for pediatric studies, awareness of symptoms, but easily tolerated).
  - Moderate: An event that causes sufficient discomfort to interfere with normal everyday activities (for pediatric studies definitely acting like something is wrong).
  - Severe: An event that prevents normal everyday activities. An AE that is assessed as severe should not be confused with an SAE. Severe is a category utilized for rating the intensity of an event; and both AE and SAE can be assessed as severe (for pediatric studies, extremely distressed or unable to do usual activities).
- Injection site redness, swelling, or hard lump from the day of vaccination through Day 14 postvaccination will be evaluated by maximum size.

#### Assessment of causality

- Did the Sponsor's product cause the AE?
- The determination of the likelihood that the Sponsor's product caused the AE will be provided by an investigator who is a qualified physician. The investigator's signed/dated initials on the source document or worksheet that supports the causality noted on the AE form, ensures that a medically qualified assessment of causality was done. This initialled document must be retained for the required regulatory time frame. The criteria below are intended as reference guidelines to assist the investigator in assessing the likelihood of a relationship between the test product and the AE based upon the available information.
- The following components are to be used to assess the relationship between the Sponsor's product and the AE; the greater the correlation with the components and their respective elements (in number and/or intensity), the more likely the Sponsor's product caused the AE:

- **Exposure:** Is there evidence that the participant was actually exposed to the Sponsor's product such as: reliable history, acceptable compliance assessment (diary, etc.), seroconversion or identification of vaccine virus in bodily specimen?
- **Time Course:** Did the AE follow in a reasonable temporal sequence from administration of the Sponsor's product? Is the time of onset of the AE compatible with a vaccine-induced effect?
- **Likely Cause:** Is the AE not reasonably explained by another etiology such as underlying disease, other drug(s)/vaccine(s), or other host or environmental factors?
- **Rechallenge:** Was the participant re-exposed to the Sponsor's product in the study?
  - If yes, did the AE recur or worsen?
  - If yes, this is a positive rechallenge.
  - If no, this is a negative rechallenge.

(Note: This criterion is not applicable if: (1) the initial AE resulted in death or permanent disability, or (2) the study is a single-dose vaccine study; or (3) Sponsor's product(s) is/are used only 1 time.)

NOTE: IF A RECHALLENGE IS PLANNED FOR AN AE THAT WAS SERIOUS AND MAY HAVE BEEN CAUSED BY THE SPONSOR'S PRODUCT, OR IF RE-EXPOSURE TO THE SPONSOR'S PRODUCT POSES ADDITIONAL POTENTIAL SIGNIFICANT RISK TO THE PARTICIPANT THEN THE RECHALLENGE MUST BE APPROVED IN ADVANCE BY THE SPONSOR CLINICAL DIRECTOR, AND IF REQUIRED, THE IRB/IEC.

- **Consistency with study intervention profile:** Is the clinical/pathological presentation of the AE consistent with previous knowledge regarding the Sponsor's product or drug class pharmacology or toxicology?
- The assessment of relationship will be reported on the CRFs/worksheets by an investigator who is a qualified physician according to his/her best clinical judgment, including consideration of the above elements.
- Use the following scale of criteria as guidance (not all criteria must be present to be indicative of a Sponsor's product relationship).
  - Yes, there is a reasonable possibility of Sponsor's product relationship:
  - There is evidence of exposure to the Sponsor's product. The temporal sequence of the AE onset relative to the administration of the Sponsor's product is reasonable. The AE is more likely explained by the Sponsor's product than by another cause.
- No, there is not a reasonable possibility of Sponsor's product relationship:

- Participant did not receive the Sponsor's product OR temporal sequence of the AE onset relative to administration of the Sponsor's product is not reasonable OR the AE is more likely explained by another cause than the Sponsor's product. (Also entered for a participant with overdose without an associated AE.)
- For each AE/SAE, the investigator must document in the medical notes that he/she has reviewed the AE/SAE and has provided an assessment of causality.
- There may be situations in which an SAE has occurred and the investigator has minimal information to include in the initial report to the Sponsor. However, it is very important that the investigator always make an assessment of causality for every event before the initial transmission of the SAE data to the Sponsor.
- The investigator may change his/her opinion of causality in light of follow-up information and send an SAE follow-up report with the updated causality assessment.
- The causality assessment is 1 of the criteria used when determining regulatory reporting requirements.

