## 3 HYPOTHESES, OBJECTIVES, AND ENDPOINTS

There is no formal hypothesis testing in this study.

Objectives	Endpoints					
Primary						
Objective: To evaluate the safety and tolerability of V114 with respect to the proportion of participants with adverse events (AEs).	
 
Following vaccination with V114:
 
Solicited injection-site AEs from Day 1 through Day 14 postvaccination
 
Solicited systemic AEs from Day 1 through Day 14 postvaccination
 
Vaccine-related serious adverse events (SAEs) through completion of study participation
 
					
• Objective: To evaluate the anti-pneumococcal polysaccharide (PnPs) serotype-specific Immunoglobulin G (IgG) Geometric Mean Concentrations (GMCs) at 30 days postvaccination (Day 30) with V114 or Prevnar 13 TM by each vaccination group.	Anti-PnPs serotype-specific IgG responses for the 15 serotypes contained in V114 at Day 30					

27-MAR-2019

V114-030-00 FINAL PROTOCOL

	Objectives	Endpoints					
Sec	condary						
•	Objective: To evaluate the safety and tolerability of PNEUMOVAX TM 23 administered 8 weeks following V114 with respect to the proportion of participants with AEs.	Following vaccination with PNEUMOVAX TM 23:  • Solicited injection-site AEs from Day 1 through Day 14 postvaccination  • Solicited systemic AEs from Day 1 through Day 14 postvaccination					
•	Objective: To evaluate the anti-PnPs serotype-specific opsonophagocytic activity (OPA) Geometric Mean Titers (GMTs) at 30 days postvaccination (Day 30) with V114 or Prevnar 13 TM by each vaccination group.	Anti-PnPs serotype-specific OPA responses for the 15 serotypes contained in V114 at Day 30					
•	Objective: To evaluate the anti-PnPs serotype-specific OPA GMTs and IgG GMCs at 30 days postvaccination with PNEUMOVAX TM 23 (Week 12) by each vaccination group.	Anti-PnPs Serotype-specific OPA and IgG responses for the 15 serotypes contained in V114 at Week 12					
Te	rtiary/Exploratory						
•	Objective: To evaluate the Anti-PnPs serotype-specific Geometric Mean Fold Rises (GMFRs) from prevaccination (Day 1) to 30 days postvaccination (Day 30) with V114 or Prevnar 13 TM for both OPA and IgG responses by each vaccination group.	Anti-PnPs serotype-specific OPA and IgG responses for the 15 serotypes contained in V114 at Day 1 and Day 30					

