# 10.3 Appendix 3: Adverse Events: Definitions and Procedures for Recording, Evaluating, Follow-up, and Reporting

#### 10.3.1 Definition of AE

#### AE definition

- An AE is any untoward medical occurrence in a clinical study participant, temporally associated with the use of study intervention, whether or not considered related to the study intervention.
- NOTE: An AE can therefore be any unfavorable and unintended sign (including an abnormal laboratory finding), symptom, or disease (new or exacerbated) temporally associated with the use of a study intervention.
- NOTE: For purposes of AE definition, study intervention (also referred to as Sponsor's product) includes any pharmaceutical product, biological product, vaccine, diagnostic agent, or protocol specified procedure whether investigational or marketed (including placebo, active comparator product, or run-in intervention), manufactured by, licensed by, provided by, or distributed by the Sponsor for human use in this study.

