# 3 ANALYTICAL AND METHODOLOGICAL DETAILS

# 3.1 Statistical Analysis Plan Summary

Key elements of the statistical analysis plan are summarized below; the comprehensive plan is provided in Sections 3.2 through 3.12.

Study Design Overview  Intervention Assignment	A Phase 3, Multicenter, Randomized, Double-blind, Active Comparator-controlled Study to Evaluate the Safety, Tolerability, and Immunogenicity of V114 Followed by Administration of PNEUMOVAX TM 23 Eight Weeks Later in Children Infected with Human Immunodeficiency Virus (HIV) (PNEU–WAY PED)  Participants will be randomly assigned in a 1:1 ratio to V114 or		
	Prevnar 13 ™ , respectively.		
Analysis Populations	Immunogenicity: Per-Protocol (PP) Safety: All Participants as Treated (APaT)		
Primary Endpoint(s)	
 
Immunogenicity:         
 
Anti-PnPs serotype-specific IgG GMCs for the 15 serotypes contained in V114 at 30 days postvaccination with V114 or Prevnar 13TM
 
 
 
Safety:         
 
Proportion of participants with solicited injection-site AEs (redness/erythema, swelling, tenderness/pain, and hard lump/induration) from Day 1 through Day 14 following V114 or Prevnar 13TM
 
Proportion of participants with solicited systemic AEs (muscle pain/myalgia, joint pain/arthralgia, headache, tiredness/fatigue, and hives or welts/urticaria) from Day 1 through Day 14 following V114 or Prevnar 13TM
 
Proportion of participants with vaccine-related SAEs through completion of study participation
 
 
 
		
Key Secondary Endpoints	
 
Immunogenicity:
 
Anti-PnPs serotype-specific OPA GMTs for the 15 serotypes contained in V114 at 30 days postvaccination with V114 or Prevnar 13TM
 
Anti-PnPs serotype-specific OPA GMTs and IgG GMCs at 30 days postvaccination with PNEUMOVAXTM23 (Week 12)
 
		

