## 3.4.2 Safety Endpoints

A description of safety measures is presented in Sections 8.3 and 8.4 of the protocol. The method of safety analysis is described in Section 3.6.2.

Safety and tolerability will be assessed by clinical review of all relevant parameters including adverse events and postvaccination temperature measurements following V114 or Prevnar 13TM and PNEUMOVAXTM23 (separately).

The safety analysis endpoints include:

- Proportion of participants with solicited injection-site AEs (redness/erythema, swelling, tenderness/pain, and hard lump/induration) from Day 1 through Day 14 postvaccination
- Proportion of participants with solicited systemic AEs (muscle pain/myalgia, joint pain/arthralgia, headache, tiredness/fatigue, and hives or welts/urticaria) from Day 1 through Day 14 postvaccination
- Proportion of participants with the broad AE categories consisting of any AE and a vaccine-related AE from Day 1 through Day 14 postvaccination
- Proportion of participants with an SAE, a vaccine-related SAE, a discontinuation due to an AE, and a death from Day 1 through Month 6 (ie, 6 months postvaccination with V114 or Prevnar 13TM)
- Proportion of participants with maximum temperature measurements meeting the Brighton Collaboration cut points from Day 1 through Day 7 postvaccination

The timeframe associated with the reporting of AEs is consistent with the collection. Nonserious adverse events (NSAEs) are reported from Day 1 through Day 14 following each vaccination. SAEs are reported from Day 1 (following vaccination with PCV [V114 or Prevnar 13TM]) through Week 8 (prior to vaccination with PPV23 [PNEUMOVAXTM23]) and from Week 8 (following vaccination with PPV23) through Month 6 (completion of study participation).

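### The sSAP ends the post-PCV SAE summary at Week 8, although the primary vaccine-related SAE endpoint runs to the end of participation, and the protocol's causality item does not name the suspected vaccine.

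*Combined protocol and SAP*

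**What the plan says.** **The endpoint.** Protocol Section 3 places "Vaccine-related serious adverse events (SAEs) through completion of study participation" among the primary endpoints that follow V114. sSAP 3.1 states it as "Proportion of participants with vaccine-related SAEs through completion of study participation". The SAE bullet in sSAP 3.4.2 runs from Day 1 to Month 6, counted from V114 or Prevnar 13. Protocol 9.6.2 also carries the SAE summary after V114 or Prevnar 13 from Day 1 to the end of participation.

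**The split.** The last paragraph of sSAP 3.4.2 reports SAEs in two periods. The first ends at Week 8, before PNEUMOVAX 23. The second runs "from Week 8 (following vaccination with PPV23) through Month 6 (completion of study participation". sSAP 3.6.2 uses the same two periods for the descriptive summaries. sSAP 3.5.2 admits a child to the analyses after PNEUMOVAX 23 only if the Visit 4 dose was given.

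**Causality.** Protocol 10.3.4 asks "Did the Sponsor's product cause the AE". The affirmative answer reads "Yes, there is a reasonable possibility of Sponsor's product relationship". Protocol 10.3.1 says that "study intervention (also referred to as Sponsor's product) includes any pharmaceutical product, biological product, vaccine", whether investigational or marketed. V114, Prevnar 13 and PNEUMOVAX 23 therefore all fall under one term.

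**The concern.** Every child is due PNEUMOVAX 23 at Visit 4, part-way through the window of the primary SAE endpoint. A programmer who follows sSAP 3.6.2 would produce a post-PCV table of vaccine-related SAEs that stops at Week 8. One who follows sSAP 3.1 or protocol 9.6.2 would produce a table that runs to the end of participation. Both could be labelled as the primary endpoint, and they can give different counts.

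The causality record, as the protocol describes it, does not help to choose between them. After Week 8 a yes is a complete answer without naming a vaccine. Under the split, a late SAE that the investigator ascribes to V114 is listed under PNEUMOVAX 23. Under the full window, a late SAE ascribed to PNEUMOVAX 23 counts in the V114 endpoint.

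Few related SAEs are to be expected, so the placement of a single event can change the reported result.

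**Working it through.** **1. The plan's own safety figures (protocol 9.9.2, sSAP 3.9.2; 200 children in the V114 group).**
- Chance of at least one SAE: 1 − (1 − p)^200. At p = 0.8% this is 79.9% (stated: 80%). At p = 0.35% it is 50.4% (stated: 50%).
- Zero-event bound: 1 − 0.025^(1/200) = 1.83% (stated: 1.82%, or 1 in 55; a rounding difference).

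The figures reproduce. None depends on how causality is assigned.

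**2. Share of the window after PNEUMOVAX 23.** The Schedule of Activities (protocol 1.3) puts Visit 4 at Day 56 to 70 after Visit 2, and the final contact at Day 166 to 194.
- Smallest share: (166 − 70)/166 = 96/166 = 57.8%.
- Largest share: (194 − 56)/194 = 138/194 = 71.1%.

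**3. What one event does.** For 0/200 the exact upper 95% limit is 1.83%. For 1/200 the estimate is 0.5%, and the limit, which solves (1 − p)^200 + 200p(1 − p)^199 = 0.025, is 2.75%. This holds for any single event. It shows only how sensitive the result is to where one event is placed.

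**4. Illustration (assumption: the documents give no distribution of SAE onset).** Take the plan's 0.8% incidence of any SAE over the whole follow-up, and let f be the fraction with onset before Visit 4. The chance of at least one SAE in the sSAP post-PCV period is 1 − (1 − 0.008f)^200.

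| Assumed onset | Chance of at least one SAE before Visit 4 |
|---|---|
| Uniform over follow-up (f = 29% to 42%, from step 2) | 37% to 49% |
| f = 50% | 55% |
| f = 75% | 70% |
| f = 90% | 76% |
| Whole follow-up (f = 100%) | 80% |

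**5. Children without PNEUMOVAX 23.** Protocol 7.1 keeps children in follow-up when study intervention is discontinued before Visit 4. The reasons allowed include an untoward effect. For an SAE after Week 8 in such a child:
- the post-PCV period of sSAP 3.6.2 has closed;
- sSAP 3.5.2 leaves the child out of the analyses after PNEUMOVAX 23.

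Neither summary clearly takes the event.

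**6. Whether the causality criteria separate the vaccines.** The time-course criterion asks "Did the AE follow in a reasonable temporal sequence from administration of the Sponsor's product" but does not say which administration. The alternative-cause criterion mentions "other drug(s)/vaccine(s), or other host or environmental factors", but PNEUMOVAX 23 is itself Sponsor's product. An investigator can weigh the two vaccines against each other, but no stated item requires the result to be recorded.

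**The case against.** The strongest reply is that the plan still contains the full-window endpoint. Protocol 9.6.2, sSAP 3.1 and the sSAP 3.4.2 bullet all count to the end of participation or Month 6, so the Week 8 split may be meant only as a display. That is a fair reading, but the sSAP does not say so. It gives the split as the rule for the summaries after each vaccination and gives no separate full-window table.

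A reader might infer more than the documents support:

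- **That a late SAE cannot be attributed to V114.** Section 10.3.4 offers its criteria as guidance. Causality is recorded on forms that are not in the documents and must also be documented in the medical notes. The form may have a field for each vaccine. The protocol text shows only that naming the vaccine is not required.
- **That the endpoint is settled by date alone.** Relatedness remains the investigator's judgement. Date decides only the period in which the sSAP lists an event.
- **That late SAEs leave the V114 results.** Summaries are by vaccination group. A late SAE in a V114 child who received PNEUMOVAX 23 appears in that group's summary after PNEUMOVAX 23. It changes period, not arm.
- **That the primary safety question fails for most of its window.** The other two primary safety endpoints, the solicited events, end at Day 14 and are untouched, as are SAEs before Week 8. Calendar share is not share of risk. Both arms are due PNEUMOVAX 23 on the same schedule, so a descriptive comparison of the arms over the whole period remains possible.

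**Conclusion.** The point holds as an inconsistency in the SAE window, with a gap in the described causality record that makes it harder to resolve. Following sSAP 3.6.2 as written would end the post-PCV summary of vaccine-related SAEs at Week 8, against the endpoint's definition. Between 58% and 71% of its calendar window would fall outside that summary. Late SAEs in children who never received PNEUMOVAX 23 have no clear place.

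The share rests only on the visit windows in protocol 1.3. The number of events affected is unknown. The study is descriptive, and no stated sample-size or precision figure changes. This is an inexpensive improvement and does not threaten the study's validity.

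**What to change.** 1. In sSAP 3.4.2 and 3.6.2, state that the primary vaccine-related SAE endpoint is reported by vaccination group from Day 1 to the end of participation, for everyone who received the Visit 2 vaccine, with or without PNEUMOVAX 23. Keep the Week 8 split as an additional display.
2. In protocol 10.3.4 and on the form, for each SAE with onset after Visit 4, record relatedness separately for the Visit 2 vaccine and for PNEUMOVAX 23, allowing both. The wording Visit 2 vaccine keeps the blind.
3. Show the full-window count by suspected vaccine.

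The cost is a few lines of text, plus one extra field if the form does not already have it. The drawback is that some late events will be recorded against both vaccines and will count under each, so the table needs a footnote saying so.

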#### Follow-up of AE and SAE

- The investigator is obligated to perform or arrange for the conduct of supplemental measurements and/or evaluations as medically indicated or as requested by Sponsor to elucidate the nature and/or causality of the AE or SAE as fully as possible. This may include additional laboratory tests or investigations, histopathological examinations, or consultation with other health care professionals.
- New or updated information will be recorded in the CRF.
- The investigator will submit any updated SAE data to the Sponsor within 24 hours of receipt of the information.

#### 10.3.5 Reporting of AEs, SAEs, and Other Reportable Safety Events to the Sponsor

# AE, SAE, and other reportable safety event reporting to Sponsor via electronic data collection tool

- The primary mechanism for reporting to the Sponsor will be the electronic data collection (EDC) tool.
  - Electronic reporting procedures can be found in the EDC data entry guidelines (or equivalent).
  - If the electronic system is unavailable for more than 24 hours, then the site will use the paper AE Reporting form.
    - Reference Section 8.4.1 for reporting time requirements.

27-MAR-2019

PRODUCT: V114
PROTOCOL/AMENDMENT NO.: 030-00

- The site will enter the SAE data into the electronic system as soon as it becomes available.
- After the study is completed at a given site, the EDC tool will be taken off-line to prevent the entry of new data or changes to existing data.
- If a site receives a report of a new SAE from a study participant or receives updated data on a previously reported SAE after the EDC tool has been taken off-line, then the site can report this information on a paper SAE form or by telephone (see next section).
- Contacts for SAE reporting can be found in the Investigator Study File Binder (or equivalent).

